6.1.4. Duration of training session in each walking mode (FirstStep, ActiveStep, ProStep)

6.1.5. Perceived rate of exertion (PRE) - Borg Perceived Rate of Exertion Scale

6.1.6. Bowel function - Modified International SCI Bowel Function Basic Data Set

6.1.7. Bladder function - Modified International SCI Lower Urinary Tract Basic Data Set

6.1.8. Frequency of secondary health conditions (urinary tract infections, pressure ulcerations, respiratory conditions)

6.1.9. Quality of life (QOL) - International SCI Quality of Life Basic Data Set

6.1.10. Functional abilities - Spinal Cord Independence Measure II (SCIM II)

6.1.11. Pain - International SCI Pain Basic Data Set (between session pain) and Modified International SCI Pain Basic Data Set (within session pain)

6.1.12. Spasticity - Modified Asworth Scale (MAS) at initial, 3, 6, 9 12 months and every 6 months thereafter

6.1.13. Strength - Upper and lower extremity motor scores (UEMS, LEMS) based on the ISNCSCI exam (Initial and 12 month and every 6 months thereafter)

6.1.14. Bone Density - DEXA Scan (Initial and 12 month)

6.2. The subject will identify an individual to spot them for safety during every moment of device use. The individual may be a relative, friend or an individual hired by the subject. The spotter will not likely be a medical professional although Ekso Bionics will consider a medical profession as a spotter. The spotter must meet the Inclusion/Exclusion criteria listed below. Ekso Bionics clinicians will train the spotter with the subject in the device over a three day period in the subject's home environment (Appendix A). The spotter must be certified as

	Protocol Name:	Investigational Study of the Ekso Bionics Powered Exoskeleton for High-Dosage Use by Individuals with Spinal Cord Injury in a Non-Clinical Environment
	Principal Investigator:	[name], Sr. Controls Engineer
	Primary Contact Name/Contact Info:	[name], Sr. Controls Engineer [contact] [contact]
	Date Revised:	9/28/2015
	Study Number:	13098-01

competent by Ekso Bionics' clinicians in order for the device to be used without an Ekso Bionics clinician present. If the spotter is not approved, the subject may locate another spotter. Due to the time commitment required of the spotter, each subject may choose to train up to two spotters during the initial spotter training sessions.

6.3. Subject training will include but is not limited to:

- 6.3.1. Informing of device functions, failure modes and common characteristics.
- 6.3.2. Safety and how to respond to various conditions including being off balance, uneven surfaces.
- 6.3.3. Device set-up and take-down
- 6.3.4. Operating the device.
- 6.3.5. Putting the device on and taking the device off.
- 6.3.6. Sitting/Standing
- 6.3.7. Walking
- 6.3.8. Balance
- 6.3.9. Using hands when in the device

6.4. Spotter training will include but is not limited to:

- 6.4.1. Informing of device functions, failure modes and common characteristics.
- 6.4.2. Safety and how to respond to various conditions including being off balance, uneven ground.
- 6.4.3. Device set-up and take-down
- 6.4.4. Operating the device.
- 6.4.5. Putting the device on and taking the device off.
- 6.4.6. Sitting/Standing
- 6.4.7. Walking
- 6.4.8. Supporting the subject

Protocol Name:	Investigational Study of the Ekso Bionics Powered Exoskeleton for High-Dosage Use by Individuals with Spinal Cord Injury in a Non-Clinical Environment
Principal Investigator:	[name], Sr. Controls Engineer
Primary Contact Name/Contact Info:	[name], Sr. Controls Engineer [contact] [contact]
Date Revised:	9/28/2015
Study Number:	13098-01

6.4.9. Helping the subject safely perform simple daily tasks inaccessible to the subject while in the device (e.g., bend down to get a plate from a cabinet or open a door)

6.5. Ekso Bionics will:

6.5.1. Evaluate the efficacy of a spotter in a home environment.
6.5.2. Evaluate the safety of using the device in a home environment.

6.6. After initial training at either Ekso Bionics or at the participant's home, a follow-up evaluation device operation may be conducted either in-person or by video at weeks 3 and 7. Review meetings will be held every three months from the time the device is delivered to the subject's home (or more frequently) to evaluate safety and efficacy. Information gathered from the study and status meetings will be used by Ekso Bionics to further the product development. Information may also be used by Ekso Bionics Marketing to determine the most appropriate market for the device and by Clinicians to aid in training future clinical staff.

Schedule of study measure.

	Baseline	3 months	6 months	9 months	12 months	Every 6 months after
Device measures (6.1.1 – 6.1.4)		✓	✓	✓	✓	✓
Physiological measures (6.1.5 – 6.1.7)	✓	✓	✓	✓	✓	✓
Frequency of secondary health conditions (6.1.8)	✓	✓	✓	✓	✓	✓

	Protocol Name:	Investigational Study of the Ekso Bionics Powered Exoskeleton for High-Dosage Use by Individuals with Spinal Cord Injury in a Non-Clinical Environment				
	Principal Investigator:	[name], Sr. Controls Engineer				
	Primary Contact Name/Contact Info:	[name], Sr. Controls Engineer [contact] [contact]				
	Date Revised:	9/28/2015				
	Study Number:	13098-01				

Quality of Life measures (6.1.9)	√	√	√	√	√	√
Functional ability (6.1.10)	√	√	√	√	√	√
Pain (6.1.11)	√	√	√	√	√	√
Spasticity (6.1.12)	√	√	√	√	√	√
Strength testing (6.1.13)	√	√	√	√	√	√
Bone Density (6.1.14)	√				√	

7. Inclusion and Exclusion Criteria

7.1. Subject Inclusion Criteria:

Participants must have a spinal cord injury between C7-L3 resulting in motor paralysis.

Participants must meet each of the remaining criteria:

7.1.1. be an experienced user of the Ekso device with a minimum of 20 hours and no more than 50 hours of device use and require no greater than minimal assist (support of up to 25% body weight) for safe and consistent walking.

7.1.1.1 no more than 2 episodes of balance loss per 1 hour training session that require no more than moderate assistance (support of 26% to 50% of body weight)

7.1.1.2 participants with more than 50 hours of device experience must agree to a 1 month period of non-use prior to acquisition of baseline measures

7.1.2. be between 18-65 years of age.

7.1.3. be able to physically fit into the exoskeleton device.

7.1.4. be able to tolerate upright standing for up to 60 minutes.

	Protocol Name:	Investigational Study of the Ekso Bionics Powered Exoskeleton for High-Dosage Use by Individuals with Spinal Cord Injury in a Non-Clinical Environment
	Principal Investigator:	[name], Sr. Controls Engineer
	Primary Contact Name/Contact Info:	[name], Sr. Controls Engineer [contact] [contact]
	Date Revised:	9/28/2015
	Study Number:	13098-01

7.1.5. have sufficient joint range of motion to fit safely within Ekso:
 Hip flexion contracture ≤ 150 ; knee flexion contracture ≤ 100 ;
 ankle dorsiflexion to neutral with no more than 10° of knee flexion.

7.1.6. have sufficient upper body strength to balance themselves with two arms

7.1.7. be fluent in English

7.2. Subject Exclusion Criteria:

7.2.1. Height below 60 inches or above 76 inches or with physical characteristics incompatible with device and testing procedure.

7.2.2. Weight above 220 lbs.

7.2.3. Lower extremity joint contractures that exceed device capacity for safe use.

7.2.4. Any medical issue that precludes full weight bearing and ambulation (e.g. osteoporosis that prevents safe standing, orthopedic injuries, pain, severe spasticity)

7.2.5. Skin integrity issues that would prevent wearing the device.

7.2.6. Cognitive and/or communicative disability inappropriate for testing as determined by Ekso Bionics clinician. Subjects must be able to follow directions well and demonstrate learning capability.

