Protocol Name:	Investigational Study of the Ekso Bionics Powered Exoskeleton for High-Dosage Use by Individuals with Spinal Cord Injury in a Non-Clinical Environment
	Principal Investigator:	[name], Sr. Controls Engineer
	Primary Contact Name/Contact Info:	[name], Sr. Controls Engineer [contact] [contact]
	Date Revised:	9/28/2015
	Study Number:	13098-01

Investigational Study of the Ekso Bionics Powered Exoskeleton for High-Dosage Use by Individuals with Spinal Cord Injury Walking in a Non-Clinical Environment

1. Investigator

Facility PI: [name], Sr. Controls Engineer, Ekso Bionics

2. Date Revised

September 28, 2015

3. Objectives

- 3.1 To determine the physiological effects of high-dosage use of the Ekso device over a 12- 36-month period.
- 3.2 To documents the quality of life benefits of using an Ekso device in a non-clinical setting.
- 3.3 To define the safety and efficacy of using the device in a home environment.
- 3.4 To determine the safety and efficacy of a non-medical professional spotting the subject.
- 3.5 To determine inclusion/exclusion criteria for an Ekso Bionics device used in a home setting.

4. Background

The incidence of spinal cord injury is estimated at 1.5-5.3 million worldwide.⁽¹⁾ "Will I walk again?" is often cited as one of the more common questions, with the decreased ability to walk as one of the most difficult challenges to live with.^(2,3) Over the last 10 years more research has focused on the ability for the spinal cord to "heal" itself, i.e. undergo plasticity,^(4,5) by task-specific, high-

	Protocol Name:	Investigational Study of the Ekso Bionics Powered Exoskeleton for High-Dosage Use by Individuals with Spinal Cord Injury in a Non-Clinical Environment
	Principal Investigator:	[name], Sr. Controls Engineer
	Primary Contact Name/Contact Info:	[name], Sr. Controls Engineer [contact] [contact]
	Date Revised:	9/28/2015
	Study Number:	13098-01

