This is a 36 month exploratory Investigational Study compliant with the NSF Human Subjects regulations (45 CFR 690) trialing a new device for the SCI populations to aid in ambulatory function in a home setting. Ekso Bionics will enable up to twelve (12) subjects with SCI to use an Ekso device in their home for a 12-month period. Qualified subjects will help Ekso Bionics determine the practical use of the device in the home environment and will enable Ekso Bionics to gather data to develop a device for use in a home environment. The study will require a trained spotter to be present at all times that the device is being used. The study will also evaluate the effectiveness of a non-medically licensed spotter to assist the subject.

6.1. The study will measure and evaluate the following to enable Ekso Bionics to determine the physiological benefits of high-dosage use of the device in the home. Baseline measures will be recorded at the beginning of the study and reassessed a minimum of every three months over a twelve month period (+/- 2 weeks) and every 6 months after (+/- 2 weeks). The metrics include:

- 6.1.1. The number of Ekso sessions completed
- 6.1.2. Number of steps taken in device (per week, average per session, whole time)
- 6.1.3. Time spent walking in device (per week, average per session, whole time)

	Protocol Name:	Investigational Study of the Ekso Bionics Powered Exoskeleton for High-Dosage Use by Individuals with Spinal Cord Injury in a Non-Clinical Environment
	Principal Investigator:	[name], Sr. Controls Engineer
	Primary Contact Name/Contact Info:	[name], Sr. Controls Engineer [contact] [contact]
	Date Revised:	9/28/2015
	Study Number:	13098-01

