Protocol Name:	Investigational Study of the Ekso Bionics Powered Exoskeleton for High-Dosage Use by Individuals with Spinal Cord Injury in a Non-Clinical Environment
Principal Investigator:	[name], Sr. Controls Engineer
Primary Contact Name/Contact Info:	[name], Sr. Controls Engineer [contact] [contact]
Date Revised:	9/28/2015
Study Number:	13098-01

The Investigational study will take place over the course of 36 months. Each subject will be evaluated for a minimum of 12 months during the 36 month period.

If at any point during the study, the subject must take a break from regular walking for medical or personal reasons, if the break is less than 2 month, they will be able to restart the study by notifying the principal investigator of the break and resuming use. If the break is greater than 2 months, the subject will need to be re-evaluated by an Ekso Bionics physical therapist to restart the study. In the case of a break of more than 2 months, the study clock will be considered "paused" at this point and the next evaluation after the initial re-evaluation will be 3 months later (+/- 2 weeks) if in the first year of the study and 6 months (+/- 2 weeks) after beyond the first year of the study.

11. Endpoints

11.1. At the conclusion of the 12-month training period, final measurements will be taken, both the subject and the non-clinical spotter will be interviewed or a questionnaire (Appendix C) will be provided to obtain information that will assist Ekso Bionics with further development of the device. Measurements will continue to be collected every 6 months for up to the conclusion of the study or the subject terminates his/her enrollment.

11.2. Sessions will be ended for any of the following reasons:

11.2.1. Subject decides to stop participation in the study at any time and for any reason.

11.2.2. An Ekso Bionics staff member stops the subject from taking part in this study at any time if he believes it is in the subject's best interest or if the subject does not follow the study protocol.

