Appendix A

- 103218 - Ekso Non-Clinical Spotter Training Schedule
- 103217 - Ekso Non-Clinical Spotter Use Training Checklist
- 103215 - Ekso Non-Clinical Spotter Competency Signoff Sheet

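### Objective 3.4: neither failed spotter certification nor spotter departure is a named outcome, so the evidence describes sponsor-certified spotters and leans towards those who stayed

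*Protocol*

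**What the plan says.** Protocol Section 3.4 sets the objective: "To determine the safety and efficacy of a non-medical professional spotting the subject". Section 6 repeats it as an aim of the design: "The study will also evaluate the effectiveness of a non-medically licensed spotter to assist the subject".

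Section 6.2 describes how a spotter enters the study. The sponsor's clinicians train the spotter with the subject over three days at home, and the spotter must then be certified as "competent by Ekso Bionics' clinicians in order for the device to be used without an Ekso Bionics clinician present". For a spotter who does not pass, the rule is: "If the spotter is not approved, the subject may locate another spotter". The same section says that "each subject may choose to train up to two spotters during the initial spotter training sessions". Most spotters are expected to be lay people, "although Ekso Bionics will consider a medical profession as a spotter".

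On assessment, Section 6.5.1 says only that the efficacy of a spotter at home will be evaluated. Section 11.1 provides that, when the 12-month training period ends, "both the subject and the non-clinical spotter will be interviewed or a questionnaire" (Appendix C) will be used. Appendix A lists a form for the certification step, the "Ekso Non-Clinical Spotter Competency Signoff Sheet" (103215).

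**The concern.** A lay person who cannot be brought to competence in the three days, or who takes on the role and gives it up, is evidence on objective 3.4. Section 6.2 handles the first case as a practical matter of finding someone else. The second case has no rule at all. Neither is listed as something the study will count.

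At stake is what the study can say at the end. If results come from certified spotters, with the one dedicated assessment given at 12 months, a favourable finding would be compatible with quite different underlying situations. Nearly every relative or friend might manage the task, or a sizeable share might not. With 2 to 12 subjects (Section 9), a few uncounted people change that picture noticeably. The finding is meant to inform development of a home device, where the difference matters.

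**Working it through.** The protocol gives no certification rate, spotter sample size or spotter success criterion, so there is no stated figure to reproduce. The check has two parts: where spotter information is collected, and how much the denominator could matter under assumed failures.

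**Where spotter information is collected**

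- Sections 6.1.1 to 6.1.14 and the schedule of measures: all items concern the subject or the device; none concerns the spotter.
- Section 6.5.1: states that spotter efficacy is evaluated, without a metric or denominator.
- Section 6.6: evaluation of device operation at weeks 3 and 7 is optional. Three-monthly reviews of safety and efficacy start from device delivery. No spotter measure is specified for either.
- Section 12.2.8: subject and spotter complete a daily log, sent at least monthly. The listed contents are sleep, departures from usual activity, other physical activity, quality of life and general impressions. The form in Appendix D is titled as a subject log.
- Section 12.3: the listed observations do not name spotter performance.
- Section 11.1 with Appendix C: the only instrument specific to the spotter that has a fixed time, at the end of the 12-month period.
- Appendix A, form 103215: records certification. No text makes its result a study outcome.

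So failed certification is not a named outcome. A spotter who leaves before 12 months has no specified exit assessment, although the logs and reviews may hold some information.

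**How much the denominator could matter**

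Input from the protocol: a maximum of 12 subjects and a minimum of 2. Assumptions: one finally certified spotter per subject, and a chance f that a candidate is not approved, the same for all candidates and independent between them. The range of f, 5% to 30%, is assumed.

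Chance of at least one failure among n first-choice spotters = 1 − (1 − f)^n:

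| f | n = 12 | n = 2 |
|---|---|---|
| 5% | 1 − 0.95^12 = 46% | 10% |
| 10% | 1 − 0.90^12 = 72% | 19% |
| 20% | 1 − 0.80^12 = 93% | 36% |
| 30% | 1 − 0.70^12 = 99% | 51% |

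Expected candidates needed for 12 certified spotters = 12/(1 − f): 12/0.9 = 13.3 at f = 10% and 12/0.7 = 17.1 at f = 30%.

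Proportion certified, with exact (Clopper-Pearson) 95% intervals:

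| Assumed failures | Approved spotters only | All spotters trained |
|---|---|---|
| 1 | 12/12 = 100% (73.5 to 100%) | 12/13 = 92.3% (64.0 to 99.8%) |
| 3 | 12/12 = 100% (73.5 to 100%) | 12/15 = 80.0% (51.9 to 95.7%) |
| 6 | 12/12 = 100% (73.5 to 100%) | 12/18 = 66.7% (41.0 to 86.7%) |

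With the minimum of 2 subjects, one failure gives 2/3 = 66.7% (9.4 to 99.2%) in place of 2/2. If all 12 subjects used the option of two spotters, three failures would give 24/27 = 88.9% (70.8 to 97.6%).

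The intervals treat the number trained as fixed, whereas training may go on until someone passes, so they are a rough guide. The middle column does not change with the number of failures, which is the point of the illustration. The protocol does not say that it will report that column.

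**The case against.** Several strong points can be made on the other side.

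- **Certification is part of what is tested, and it protects the subject.** Section 6 requires a trained spotter at all times, and Section 17.2 rests the device's risk classification on the spotting requirement. An unapproved candidate never spots without a clinician present, so yields no unsupervised outcome. This stands: the gate is not at fault. It also means that the home evidence concerns certified spotters, which the wording of 3.4 does not say.
- **A reader might infer that spotters replaced mid-study are never scored.** The protocol does not support this. The replacement sentence in 6.2 concerns approval at certification only, and no mid-study replacement rule exists. Section 7.3.7 expects availability throughout the study. A certified spotter who leaves will normally have contributed to daily logs and perhaps to the reviews. The content of the sign-off sheet is not shown, so it cannot be said that non-approval goes unrecorded.
- **A reader might infer that 3.4 will be judged only on spotters who lasted.** No analysis set or exclusion rule says so.
- **A statistical analysis plan could define the denominator.** It could, and that part alone would not be a finding. It could not recover an exit questionnaire that was never given, because the protocol fixes when that form is used.
- **This is an exploratory pilot with no pass mark for spotters.** This limits the weight of the point to a cheap improvement.

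**Conclusion.** The point holds in a limited form. The protocol allows replacement of spotters who are not approved, with no stated cap. It names neither certification failure nor spotter discontinuation as an outcome, and it times its one spotter-specific instrument at the end of the 12-month period. Evidence for objective 3.4 therefore applies to sponsor-certified spotters and tends to favour those who stayed.

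The size is unknown, because the documents give no failure or departure rate; the percentages above rest on assumed values. The lean towards those who stayed also assumes that some departures are linked to how the spotting went, for example through the musculoskeletal injury named as a risk in 16.8. A departure for unrelated reasons would lose information without a clear direction.

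The documents do not support the claim that the study will report lay spotters as uniformly trainable, or that failed or departed spotters are excluded. This is a cheap improvement to what is collected and how the conclusion is worded.

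**What to change.** 1. In Section 6.5.1, state that the evaluation covers every lay spotter who starts the three-day training. Report how many started, were certified, were not approved and were later discontinued, with reasons, using all lay spotters trained as the denominator. The sign-off sheet (103215) can supply the certification result. Tabulate any medical professional acting as spotter separately, since that person does not inform 3.4.
2. In Section 11.1, give the Appendix C questionnaire (103223) when a spotter leaves as well as at 12 months.
3. Word the 3.4 conclusion as applying to certified lay spotters, and give the certification rate beside it. Because 7.3 and the interviews in 8.2 select candidates before training, say that the rate describes people who had passed that screening.

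The certification requirement itself is left unchanged. The cost is a tally and an occasional earlier questionnaire on forms that already exist. The downside is this slight extra data collection and a spotter result that may look less favourable.

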7.2.7. Pregnancy (Self-reported)

7.2.8. Colostomy

7.2.9. Medical or environmental conditions arising after the start of the study that are deemed unsafe per Ekso Bionics discretion.

7.3. Spotter Inclusion Criteria:

Spotters must meet each of the remaining criteria:

7.3.1. be between 18-65 years of age.

7.3.2. be physically fit and

	Protocol Name:	Investigational Study of the Ekso Bionics Powered Exoskeleton for High-Dosage Use by Individuals with Spinal Cord Injury in a Non-Clinical Environment
	Principal Investigator:	[name], Sr. Controls Engineer
	Primary Contact Name/Contact Info:	[name], Sr. Controls Engineer [contact] [contact]
	Date Revised:	9/28/2015
	Study Number:	13098-01

- 7.3.3. able to lift and carry the Ekso device (50 pounds).
- 7.3.4. able to support the subject if off balance.
- 7.3.5. able to guide the subject to a safe position in case of a fall.
- 7.3.6. be certified in First Aid
- 7.3.7. be available at least four days per week for at least five out of every six weeks throughout the duration of the study. If more than one spotter will be working with the subject, then spotters together must meet these criteria.
- 7.3.8. be fluent in speaking and reading English
- 7.3.9. be able to read the LCD display
- 7.3.10. be able to hear device alarms and tones

7.4. Spotter Exclusion Criteria:

- 7.4.1. Known muscular-skeletal or other medical condition that could cause regular delays of the study if spotter is injured or impaired.
- 7.4.2. Pregnancy (Self-Reported)

Protocol Name:	Investigational Study of the Ekso Bionics Powered Exoskeleton for High-Dosage Use by Individuals with Spinal Cord Injury in a Non-Clinical Environment
Principal Investigator:	[name], Sr. Controls Engineer
Primary Contact Name/Contact Info:	[name], Sr. Controls Engineer [contact] [contact]
Date Revised:	9/28/2015
Study Number:	13098-01

Environmental Condition Requirements

Use of the device must adhere to the following conditions:

Environment	
General Specifications	
 Not for use in damp areas Solid, flat terrain with less than 2% slope Not for use on deep pile carpet (over $\frac{1}{2}$" pile), ice, loose dirt or gravel, grass, rubber or high friction flooring, and other similar surfaces
Conditions of Visibility	For Control Pad: 
 Ambient luminance range: 100lx to 1500lx Viewing distance: 20-30 cm Viewing angle: normal to display +/- 45 deg
Physical Conditions	
 Temperature range 10-30 deg C Relative humidity range 20-95%, non-condensing Background sound pressure level: <70 dBA in the range of 100 Hz
Frequency of Use for Operator	
Maximum Frequency	6 hours per day

8. Recruitment Methods

8.1. Ekso Bionics will locate interested subjects from an existing group of prior test subjects. Additional networking for the purpose of identifying potential subjects will occur through rehabilitation hospitals currently using the Ekso Bionics device as well as non-for-profit organizations interested in supporting the individual use of Ekso. Since all recruitment will be verbal,

Protocol Name:	Investigational Study of the Ekso Bionics Powered Exoskeleton for High-Dosage Use by Individuals with Spinal Cord Injury in a Non-Clinical Environment
Principal Investigator:	[name], Sr. Controls Engineer
Primary Contact Name/Contact Info:	[name], Sr. Controls Engineer [contact] [contact]
Date Revised:	9/28/2015
Study Number:	13098-01

recruitment flyers or other marketing materials are not necessary. Hospitals acting as recruiting centers to locate Ekso Bionics test subjects may have their own IRB for recruiting only.

8.2. Ekso Bionics Clinical team members will perform the initial screening of potential participants. The team will determine study eligibility based on a clinical evaluation, home site evaluation, interviews with the prospective non-clinical spotter(s) and the experience and capability of the subject. They will discuss in detail the objectives, complete protocol, and its risks and potential benefits.

8.3. Once volunteers agree to participate they will be required to provide a medical release from their physician. Potential participants will read the Ekso Bionics informed consent and have an opportunity to ask questions and discuss the study with their physician, family, and friends before agreeing to enter the study. The informed consent and medical release (Appendix B) also include contact information should the participant or his/her associates have any questions. The original signed informed consent will be given to the participant, and a copy will be kept in a locked cabinet at Ekso Bionics accessible only by Investigators.

9. Number of Subjects

The study will consist of a minimum of two (2) subjects and a maximum of twelve (12).

10. Study Timelines

Protocol Name:	Investigational Study of the Ekso Bionics Powered Exoskeleton for High-Dosage Use by Individuals with Spinal Cord Injury in a Non-Clinical Environment
Principal Investigator:	[name], Sr. Controls Engineer
Primary Contact Name/Contact Info:	[name], Sr. Controls Engineer [contact] [contact]
Date Revised:	9/28/2015
Study Number:	13098-01

The Investigational study will take place over the course of 36 months. Each subject will be evaluated for a minimum of 12 months during the 36 month period.

If at any point during the study, the subject must take a break from regular walking for medical or personal reasons, if the break is less than 2 month, they will be able to restart the study by notifying the principal investigator of the break and resuming use. If the break is greater than 2 months, the subject will need to be re-evaluated by an Ekso Bionics physical therapist to restart the study. In the case of a break of more than 2 months, the study clock will be considered "paused" at this point and the next evaluation after the initial re-evaluation will be 3 months later (+/- 2 weeks) if in the first year of the study and 6 months (+/- 2 weeks) after beyond the first year of the study.

11. Endpoints

11.1. At the conclusion of the 12-month training period, final measurements will be taken, both the subject and the non-clinical spotter will be interviewed or a questionnaire (Appendix C) will be provided to obtain information that will assist Ekso Bionics with further development of the device. Measurements will continue to be collected every 6 months for up to the conclusion of the study or the subject terminates his/her enrollment.

11.2. Sessions will be ended for any of the following reasons:

11.2.1. Subject decides to stop participation in the study at any time and for any reason.

11.2.2. An Ekso Bionics staff member stops the subject from taking part in this study at any time if he believes it is in the subject's best interest or if the subject does not follow the study protocol.

